6.3. Measures to Minimize Bias: Randomization and Blinding

Randomization and stratification

All participants will be centrally assigned to randomized study intervention using an IWRS. Before the study is initiated, the login information and directions for the IWRS will be provided to each site.

Participants will be randomly assigned in an 1:1 ratio to LY3209590: insulin degludec.

Participants will be stratified based on

- country
- HbA1c stratum at Visit 1 (<8% and \geq 8%)
- sulfonylurea use at randomization (Yes/No), and
- GLP-1 RA use at randomization, regardless of oral or injectable administration (Yes/No).

Blinding

This is an open-label study. Investigators and participants will be unblinded to the assigned treatment groups.

The Lilly study team members who are closely involved in data interpretation and analysis planning will remain blinded throughout the course of the study. Only a minimum number of Lilly personnel will see the randomization table and treatment assignments before the study is complete.

The investigator should make every effort to preserve the blinding when contacting the Lilly study team members, including the Lilly clinical research physician or scientist.

Unblinded reviews

External committees reviewing unblinded data during the study are described in Section 10.1.5.

An early PK/PD unblinded transfer may also be conducted. Only a small group of personnel can be unblinded to the data for the potential PK/PD analysis and must keep information confidential until the planned unblinding of the trial.

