9.3.3. Secondary Endpoints Analysis

9.3.3.1. Multiplicity-Adjusted Endpoints

A graphical approach will be used to control the overall type I error for the primary objective and testing of key secondary objectives as described in Section 9.1.

Noninferiority test

The noninferiority test in change from baseline to Week 52 (Visit 31) in HbA1c for the subpopulations will be based on the ANCOVA model for treatment regimen estimand (using data from the EAS1) and an MMRM model for efficacy estimand (using data from the EAS2).

In the ANCOVA model, treatment, strata (country and SU use at randomization), and baseline of the dependent variable will be used as covariates.

The MMRM model will include treatment, strata (country and SU use at randomization), visit and treatment-by-visit interaction as fixed effects, and baseline of the dependent variable as a covariate.

For the treatment regimen estimand, the missing data will be imputed by multiple imputation with the approach similar to the imputation used for the primary endpoint.

Superiority test

The superiority test in change from baseline to Week 52 (Visit 31) in HbA1c will be based on the same primary endpoint analysis described above.

The time in glucose range between 70 and 180 mg/dL (3.9 and 10.0 mmol/L) inclusive, measured by CGM, will be analyzed using an ANCOVA model for treatment regimen estimand and an MMRM model for efficacy estimand. In the ANCOVA model, treatment, strata (country, baseline HbA1c stratum [$<8.0\%$, $\geq 8.0\%$], GLP-1 RA treatment at randomization, and SU use at randomization), and baseline of the dependent variable will be used as covariates. The MMRM model will include treatment, strata (country, baseline HbA1c stratum [$<8.0\%$, $\geq 8.0\%$], GLP-1 RA treatment at randomization, and SU use at randomization), visit and treatment-by-visit interaction as fixed effects, and baseline of the dependent variable as a covariate. For treatment regimen estimand, the missing data will be imputed by multiple imputation with the approach similar to the imputation used for the primary endpoint.

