1.2. Study Design

- This is a Phase 3, parallel-design, open-label, randomized control study to evaluate the efficacy and safety of LY3209590 administered once-weekly compared to insulin degludec administered daily.
- The study includes a 3-week screening and lead-in period, a 52-week treatment period, and a safety follow-up period approximately 5 weeks after the last visit in the treatment period.
- Assignment to treatment groups will be determined by an interactive web-response system (IWRS). Participants will be randomly assigned to 1 of the 2 treatment groups in 1:1 ratio (LY3209590: insulin degludec) at Visit 3 (Week 0). The number of participants in each subpopulation of participants using or not using GLP-1 RA will be approximately 50% of the study population with balanced treatment assignment. Stratification will be by country, HbA1c stratum at Visit 1 (Week -3) (<8.0%, ≥8.0%), sulfonylurea use at randomization, and GLP-1 RA use at randomization, regardless of oral or injectable administration.
- Rescue therapy will be considered during the treatment period if the participants meet the protocol criteria of severe, persistent hyperglycemia.
- If study intervention is permanently discontinued, the participant will be encouraged to continue participation in the study for continued monitoring. Both efficacy (including HbA1c) and safety data will continue to be collected per the schedule of activities in the protocol.
- Participants will collect blinded CGM for 2 weeks prior to Visit 3 (Week 0), for 4 weeks prior to Visit 7 (Week 4), Visit 15 (Week 12), Visit 24 (Week 26), Visit 31 (Week 52), and for 4 weeks after Visit 31 (Week 52). Dexcom G6 system provides readings every 5 minutes. In China, instead of the Dexcom G6 system, the Libre Freestyle H system which provides readings every 15 minutes will be used. Main analyses for CGM measurements will be conducted based on data from the Dexcom G6 system.

2. Statistical Hypotheses

Primary Hypothesis

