For categorical measures, summary statistics will include sample size, frequency, and percentages. Fisher's exact test or logistic regression will be used for treatment comparisons, unless otherwise stated. For laboratory values, both conventional (CN) and System International (SI) units will be presented. Therefore, both % and mmol/mol will be presented for HbA1c and both mg/dL and mmol/L will be presented for glucose measurements.

In this study, the negative binomial regression will be used to analyze the number of hypoglycemic episodes. Group Mean instead of LS mean will be estimated and delta method will be used to estimate the standard error of the Group Mean (Qu and Luo 2015). Group Mean is defined as the mean response in the treatment group for the studied population. The difference between LS mean and the Group Mean is that LS mean estimates the response by taking the

inverse link function on mean covariates, while the Group Mean takes the inverse link function on individual patient covariates first and then averages over all patients. For Level 2 hypoglycemia and severe hypoglycemia, the empirical method based on exposure adjusted rate (calculated by total number of events divided by total exposure) may be used for the treatment comparison if the number of episodes is too small and leads to convergency issues in the negative binomial regression model.

Below table describes the definition of baseline and post-baseline observations for different analyses.

Analysis	Baseline Observations	Post-Baseline Observations
HbA1c (treatment regimen estimand)	The baseline is the last non-missing assessment prior to or at the first day of study treatment.	Planned measurements at Visit 24 (secondary endpoint, Week 26) and Visit 31 (primary endpoint, Week 52) in EAS1. Use unplanned measurements if no planned measurement. Multiple imputation approach will be used to impute missing observations at Visit 24 (Week 26) and Visit 31 (Week 52).
HbA1c (efficacy estimand)	The baseline is the last non-missing assessment prior to or at the first day of study treatment.	Visit 5, 7, 15, 17, 24, 27, and 31 (Weeks 2, 4, 12, 16, 26, 36, and 52) in EAS2 for MMRM. Planned measurements at scheduled visits will be included. Use unplanned measurements if no planned measurements.

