4.4.1.2. Main analytical approach

The non-inferiority test in change from baseline to Week 52 (Visit 31) in HbA1c for each of the subpopulations with participants using or not using GLP-1 RA will be analyzed. For the treatment regimen estimand (using data from the EAS1), for each subpopulation, the missing data will be imputed by multiple imputation with the approach similar to the imputation used for the primary endpoint. The imputed data for that subpopulation will be analyzed by the ANCOVA model using treatment, strata (country and SU use at randomization), and baseline HbA1c as independent variables. For the efficacy estimand (using data from the EAS2), the MMRM model which includes treatment, strata (country and SU use at randomization), visit and treatment-by-visit interaction as fixed effects, and baseline HbA1c as a covariate will be used, with data from that subpopulation.

The superiority test in change from baseline to Week 52 (Visit 31) in HbA1c will be based on the same primary endpoint analysis described in Section [4.3.2](#).

The time in glucose range between 70 and 180 mg/dL inclusive measured by CGM will be analyzed using an ANCOVA model for treatment regimen estimand and an MMRM model for efficacy estimand. CGM Primary Analysis Population will be used for the analyses. The analyses are similar to the primary analysis described in Section 4.3.2 with additional term of baseline HbA1c stratum ($<8.0\%$, $\geq 8.0\%$) in analysis models. For treatment regimen estimand, only participants with an observation at baseline or at Week 52 will be included in the analysis. the missing data at Week 52 will be imputed by multiple imputation with the approach similar to the imputation used for the primary endpoint. The missing baseline will be imputed using multiple imputation under assumption of missing at random.

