4.4.2. Supportive secondary Endpoint(s)

4.4.2.1. Other Efficacy Endpoints

The analysis of change from baseline for HbA1c at Week 26, fasting glucose by SMBG at Week 26 and 52, CGM (except for variability) parameters at Week 26 and 52 will be performed for both treatment regimen estimand and efficacy estimand. The analyses for other supportive efficacy endpoints will be based on the EAS2 data.

For treatment regimen estimand, only participants with an observation at baseline or at the endpoint visit will be included in the analysis. The missing baseline will be imputed using multiple imputation under assumption of missing at random. Missing data at the endpoint visit will be imputed using either retrieved dropout or return-to-baseline multiple imputation approach determined by the criterion described for the primary efficacy endpoint in Section 4.3.2. ANCOVA analysis will be conducted similar to that for the primary endpoint. An additional term of baseline HbA1c stratum ($<8.0\%$, $\geq 8.0\%$) will be added into the model for the endpoints other than HbA1c.

For efficacy estimand, participants with baseline and at least one post baseline observation will be included in the analysis. The longitudinal observations of actual and change from baseline in HbA1c to Week 26 will be analyzed using the same MMRM model as for the efficacy estimand described in Section 4.3.2. The analyses of other continuous efficacy measures (fasting glucose, insulin dose and CGM parameters) will use an MMRM model similar to that for the primary endpoint with an additional term of baseline HbA1c stratum ($<8.0\%$, $\geq 8.0\%$). The variance-covariance structure in the MMRM models for fasting glucose from SMBG and insulin dose will be based on compound symmetry.

Longitudinal logistic regression model with baseline value, strata (country, GLP-1 use at randomization, SU use at randomization and baseline HbA1c stratum [$<8.0\%$, $\geq 8.0\%$]), Treatment, Time, and Treatment-by-time interaction as factors will be used for analysis for CGM targets of glycemic control. See Section 4.3.2 for variance-covariance structure selection.

The time point for primary CGM data analysis is CGM session. In addition, the average time in glucose range, hypoglycemia range and hyperglycemia range by week (by visit for treatment period) will be summarized by treatment. Average daily time within each range since last dose

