6.1. Appendix 1: Demographic and Baseline Characteristics

Demographic and baseline characteristics including but not limited to age (years), age groups (<65 , ≥ 65 and <75 , ≥ 75 and <85 , ≥ 85 years), sex, ethnicity, race, country, region, height, weight (kg), body mass index (BMI: kg/m²), BMI groups (<25 , ≥ 25 and <30 , ≥ 30 and <35 , ≥ 35 kg/m²), eGFR groups (<30 , ≥ 30 and <60 , ≥ 60 and <90 , ≥ 90 mL/min/1.73 m²), eGFR categories by SU use, duration of diabetes (years), HbA1c at screening, HbA1c stratum at screening ($<8.0\%$ and $\geq 8.0\%$), baseline HbA1c, baseline HbA1c stratum ($<8.0\%$ and $\geq 8.0\%$), fasting serum glucose (mmol/L and mg/dL), GLP-1 RA treatment at randomization, SU use at randomization and number of non-insulin antihyperglycemic medication use at randomization will be summarized by treatment group using the mITT and Randomized Population (if different from the mITT).

Continuous measures will be summarized using descriptive statistics and treatment difference will be analyzed using the analysis of variance. Categorical measures will be summarized using sample size, frequency, and percentage and treatment difference will be analyzed using Chi-squared test.

The by-participant listing of demographic and baseline characteristics will be provided for Randomized Population.

Historical conditions are conditions that end prior to inform consent and preexisting conditions are conditions that are still ongoing at inform consent. The number and percentage of participants with historical conditions will be summarized by treatment group using MedDRA PT using the mITT and Randomized Population (if different from the mITT). Events will be ordered by decreasing frequency within SOC. Similar summary will also be provided for preexisting conditions.

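### Time-in-range, fasting-glucose, insulin-dose, CGM and patient-reported models adjust for a re-cut baseline HbA1c group instead of the Visit 1 randomization stratum, and leave out continuous baseline HbA1c: a small precision and consistency point, not bias.

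*SAP*

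**What the plan says.** **Randomization.** Protocol 6.3 lists the "HbA1c stratum at Visit 1" (below 8% versus 8% or more) as a stratification factor, with country, sulfonylurea use and GLP-1 RA use. SAP 1.2 says the same and places Visit 1 at Week -3.

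**Baseline.** For HbA1c, SAP 4.1 states: "The baseline is the last non-missing assessment prior to or at the first day of study treatment". The Schedule of Activities draws HbA1c at Visits 1 and 3 before treatment starts, so baseline is normally Visit 3 and falls back to Visit 1 only if the later sample is missing.

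**Two variables.** SAP Appendix 1 (6.1) lists "HbA1c at screening, HbA1c stratum at screening" and then, as separate items, baseline HbA1c and its stratum.

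**Models that use the baseline stratum**
- Time in range: Protocol 9.3.3.1 ("In the ANCOVA model, treatment, strata (country, baseline HbA1c stratum", and likewise in the MMRM) and SAP 4.4.1.2 ("with additional term of baseline HbA1c stratum").
- Supportive fasting glucose, insulin dose and CGM endpoints: SAP 4.4.2.1 ("An additional term of baseline HbA1c stratum").
- TRIM-D, SF-36 and EQ-5D-5L: SAP 4.4.2.3.
- CGM event duration during treatment: SAP 4.6.3.1.2.

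**Models that do not**
- Hypoglycemia rate and incidence use baseline HbA1c itself (SAP 4.6.3.1).
- Modelled laboratory measures, weight and vital signs have no HbA1c term (SAP 4.6, 4.6.3.4).
- HbA1c models carry continuous baseline HbA1c as the baseline of the dependent variable (SAP 4.3.2).

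**The concern.** Several of the affected models list the term inside the strata, beside country, GLP-1 RA use and SU use, which are the randomization factors. HbA1c is the exception: the randomized factor has been replaced by a category re-derived from a later sample, and neither document says why. A programmer reading it as a stratum would take the Visit 1 value from the IWRS; one reading it as baseline would re-cut the Visit 3 value. Time in range is a multiplicity-controlled test, so its model should be unambiguous.

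The term also reduces a continuous predictor to two groups. For time in range the loss is cushioned by the endpoint's own baseline. Insulin dose has no baseline covariate (SAP 4.1 marks it not applicable), so the two-group term is the only glycemic adjustment in that model.

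**Working it through.** **1. Reproduce the plan's figure (Protocol 9.5, SAP 5).** Inputs: 377 completers per arm, SD 18%, difference 5%, alpha 0.05 taken as two-sided.
- Completers: 888 × 0.85 / 2 = 377.4 per arm.
- SE = 18 × √(2/377) = 1.311.
- Power = Φ(5/1.311 − 1.960) = Φ(1.854) = 96.8%. The stated figure of at least 95% holds.

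**2. How often do the two groups differ?** The documents give no HbA1c mean or SD. Assumed: true HbA1c normal with mean 8.2 and SD 0.9, independent within-person error at each visit, and Visit 1 restricted to 7.0–10.5 (inclusion criterion 3). By simulation:

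| Within-person SD | In a different group at Visit 3 |
|---|---|
| 0.15 | 8.0% |
| 0.20 | 10.7% |
| 0.25 | 13.2% |
| 0.30 | 15.8% |

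A within-person SD of 0.35, with values rounded to one decimal, gives 17.7%.

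**3. How much of continuous baseline HbA1c does each split carry?** Same assumptions, within-person SD 0.15 to 0.30, squared correlation with Visit 3 HbA1c:
- Visit 3 split (as planned): about 0.60 throughout.
- Visit 1 split: 0.55, falling to 0.44.

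The textbook 2/π = 64% applies to a median split of a normal variable. Here about 65% of participants are at or above 8.0%, so 60% is the better figure.

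**4. Effect on time-in-range power.** Replace 18 by 18 × √(1 − R²), where R² is the share of Week 52 time-in-range variance explained by the HbA1c term. Assumed: a partial correlation r of 0.1 to 0.4 between Week 52 time in range and Visit 3 HbA1c, and an SD of 18% that applies before this term is fitted. Example with the continuous covariate at r = 0.4: R² = 0.16, SD = 18 × √0.84 = 16.50, SE = 16.50 × √(2/377) = 1.202, power = Φ(5/1.202 − 1.960) = 98.6%.

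| HbA1c term | r = 0.1 | r = 0.4, within-person SD 0.15 / 0.25 / 0.35 |
|---|---|---|
| Visit 1 stratum alone | 96.9% | 97.9 / 97.8 / 97.6% |
| Visit 3 stratum (planned) | 96.9% | 98.0 / 98.0 / 98.0% |
| Continuous baseline HbA1c | 96.9% | 98.6 / 98.6 / 98.6% |

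The widest gap is 98.6 − 97.6 = 1.0 point. Against the planned term, the continuous covariate gains at most 98.6 − 98.0 = 0.6 point. In this set-up the outcome depends on HbA1c only through the Visit 3 value, so adding the Visit 1 stratum to the continuous covariate leaves the last row unchanged.

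**The case against.** The plan can be defended on several grounds, and most of them stand.

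- **Validity.** A reader might infer that the tests are biased because the model does not mirror the randomization. The documents do not support that. The term is measured before treatment, so adjusting for it does not bias the comparison. Omitting the exact stratifier tends at most to make a test slightly conservative.
- **Direction.** A reader might expect the Visit 1 stratum to recover precision by itself. Steps 3 and 4 show the reverse: the planned Visit 3 split is the slightly better predictor. Any gain comes from the continuous covariate.
- **Scope.** It is tempting to say that the plan throws away the continuous baseline, or that all non-HbA1c endpoints are affected. Neither is so. The endpoint's own baseline stays in the model where there is one, and hypoglycemia rate and incidence, laboratory, weight and vital-sign models are untouched.
- **Source.** For time in range the SAP follows Protocol 9.3.3.1; it does not depart from it.
- **Insulin dose.** Participants are insulin naive, so a missing baseline dose is expected and is not an oversight. Even so, baseline HbA1c remains available as a covariate there.

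The objection does not explain why the HbA1c randomization factor alone was replaced, or why a continuous value already used in the hypoglycemia models was cut in two here.

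**Conclusion.** The point holds as a minor one. In the listed models the HbA1c term is, on the natural reading of SAP 4.1 and Appendix 1, a re-cut baseline category. It is not the factor used to randomize, and continuous baseline HbA1c is absent. That the value is normally from Visit 3 is inferred from the baseline definition and the Schedule of Activities; neither document says it outright.

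The effect is on precision and consistency. Some 8% to 16% of participants would sit in a different group from the one they were randomized in, about 40% of the linear information in baseline HbA1c is lost to the cut, and time-in-range power shifts by at most about 1 point from a comfortable starting level. All three figures rest on assumed HbA1c distributions, and the last also on an assumed correlation. The gain is most plausible for insulin dose, but the documents give nothing from which to size it.

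**What to change.** In the models of SAP 4.4.1.2, 4.4.2.1, 4.4.2.3 and 4.6.3.1.2 (duration) that now carry the baseline HbA1c stratum, make two changes together:

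1. Replace that stratum with the Visit 1 HbA1c stratum recorded in the IWRS.
2. Add continuous baseline HbA1c as a covariate.

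Do not make the first change alone, because it would slightly reduce precision. Sections that borrow these models, such as SAP 4.5.2 (continuous endpoints) and 4.7.2.1 (insulin dose and CGM), then follow by cross-reference.

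For time in range this departs from Protocol 9.3.3.1. SAP 4.9, which now reports no changes, must record it with a reason. The sponsor should confirm that it is not a change to a principal feature requiring an amendment under Protocol 9.3.1. If the sponsor keeps the current models, one sentence should say which HbA1c value defines the stratum and why it is dichotomized.

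The cost is SAP text and minor reprogramming before unblinding. Both variables are already collected, and each model gains one parameter.

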4.4.1.3. Sensitivity Analysis

The analyses described in Section 4.4.1.2 will be repeated for both the treatment regimen estimand and efficacy estimand by including inadvertent enrolled participants using mITT population.

4.4.2. Supportive secondary Endpoint(s)

4.4.2.1. Other Efficacy Endpoints

The analysis of change from baseline for HbA1c at Week 26, fasting glucose by SMBG at Week 26 and 52, CGM (except for variability) parameters at Week 26 and 52 will be performed for both treatment regimen estimand and efficacy estimand. The analyses for other supportive efficacy endpoints will be based on the EAS2 data.

For treatment regimen estimand, only participants with an observation at baseline or at the endpoint visit will be included in the analysis. The missing baseline will be imputed using multiple imputation under assumption of missing at random. Missing data at the endpoint visit will be imputed using either retrieved dropout or return-to-baseline multiple imputation approach determined by the criterion described for the primary efficacy endpoint in Section 4.3.2. ANCOVA analysis will be conducted similar to that for the primary endpoint. An additional term of baseline HbA1c stratum ($<8.0\%$, $\geq 8.0\%$) will be added into the model for the endpoints other than HbA1c.

For efficacy estimand, participants with baseline and at least one post baseline observation will be included in the analysis. The longitudinal observations of actual and change from baseline in HbA1c to Week 26 will be analyzed using the same MMRM model as for the efficacy estimand described in Section 4.3.2. The analyses of other continuous efficacy measures (fasting glucose, insulin dose and CGM parameters) will use an MMRM model similar to that for the primary endpoint with an additional term of baseline HbA1c stratum ($<8.0\%$, $\geq 8.0\%$). The variance-covariance structure in the MMRM models for fasting glucose from SMBG and insulin dose will be based on compound symmetry.

Longitudinal logistic regression model with baseline value, strata (country, GLP-1 use at randomization, SU use at randomization and baseline HbA1c stratum [$<8.0\%$, $\geq 8.0\%$]), Treatment, Time, and Treatment-by-time interaction as factors will be used for analysis for CGM targets of glycemic control. See Section 4.3.2 for variance-covariance structure selection.

The time point for primary CGM data analysis is CGM session. In addition, the average time in glucose range, hypoglycemia range and hyperglycemia range by week (by visit for treatment period) will be summarized by treatment. Average daily time within each range since last dose

by CGM Session during treatment period will also be summarized for LY3209590. Missing data patterns will be summarized at daily, weekly (visit) and CGM session levels.

For CGM parameters, data from participants in China using Libre Freestyle H system will be analyzed separately ([Appendix 6](#) [Section 6.6]).

The analysis of study insulin dose will use an MMRM model on the EAS2 data with treatment, strata (country, GLP-1 RA treatment at randomization, SU use at randomization, and baseline HbA1c stratum [$<8.0\%$, $\geq 8.0\%$]), visit and treatment-by-visit interaction as covariates. The average weekly dose during each visit for individual participants will be used in the analysis. In the LY3209590 group, the average dose of each visit (that is, average of weekly doses since last visit) will be used as the average weekly dose. In the insulin degludec group, the average weekly dose will be calculated by the average daily dose multiplying by 7. The analysis will be repeated for average daily dose in U and daily dose in U/kg. The body weight at the visit will be used to calculate the daily dose in U/kg at the same visit.

